Background: Transcatheter Aortic Valve Implantation (TAVI) is a method where an artificial heart valve is implanted through a. femoralis (the groin) or via alternative access (apical, trans caval, axillaris, direct aorta), instead of conventional surgery. TAVI is the routine treatment for in-operable and high-surgical risk patients, and is increasingly used in patients with low and intermediate surgical risk (1, 2). In Denmark, approximately 1000 TAVI valves are implanted each year. In Europe yearly implantation mounts to more than 50.000 TAVI devices. Although a considerable number of TAVI valves have been introduced, there are few direct comparisons of the valves. The 5 most widely used valves are: Sapien (Edwards)(2), Evolut (Medtronic) (3), Navitor/Portico (Abbott) (4, 5) and Acurate (Boston) (6, 7). New TAVI-valves are routinely introduced to the market. Recently, Myval (Meril) (8) and Allegra (New Valve Technology) (9) were launched.

The larger TAVI-centers are routinely using 2-4 different valves, and the majority of patients are eligible for treatment with more than one valve.

The purpose of the “Compare-TAVI” organization is to ensure a continuous comparison of the TAVI-valves implanted, and to monitor long-term valve performances.

Purpose: To compare outcome in patients randomized to treatment with one of two TAVI-valves.

Hypotheses:

1. There is no difference in the combined endpoint (death, stroke, moderate/severe para-valvular leakage, moderate/severe valve deterioration) between the two valves being compared.
2. There is no difference between valves in secondary endpoints: death, stroke, moderate/major paravalvular leakage, moderate/severe valve deterioration, new pacemaker implantation, readmission for congestive heart failure, 6-minute walk test, and degeneration of the valve as evaluated by

computerized tomography (CT), transthoracic echocardiography (TTE), transesophageal echocardiography (TEE), or MRI.

Design: Randomized controlled trial with clinical and national registry follow-up.

Inclusion criteria:

1. Patient more than 18 years of age.
2. Patient eligible for at least 2 valves being implanted routinely at the participating center, according to a TAVI heart team conference.
3. The center experience for each of the valves considered should be more than 15 cases a year, and the treating physician should have implanted at least 15 of each valves used in the trial.
4. The center volume should be more than 75 cases a year.
5. The patient has given signed informed consent.
6. TAVI performed via the femoral artery.

Centers eligible for inclusion: Scandinavian and European centers who fulfill the above mentioned criteria.

Randomization:

Before randomizing patients, the center decides which two valves the patient is found eligible for, and enters these valves in the electronic randomization form (TrialPartner). Randomization is then performed between these two valves. A patient is only randomized if a dedicated technical TAVI conference has found the patient eligible for treatment with both valves.

Consecutive cohorts are established.

We plan to initiate the following cohorts:

Cohort A: Patients randomized to the Sapien or the Accurate neo 2 TAVI valve (Approved, not recruiting, await funding).

Cohort B: Patients randomized to the Sapien or the Myval TAVI valve (Recruiting).

Cohort C: Patients randomized to a BEV valve (To be determined whether Sapien or Myval) compared to the Navitor valve (Awaits approval and funding).

Operator requirements:

Any procedure requires that the physician has performed at least 15 implantations with the valve in use. Otherwise the procedure is performed according to the routine of the institution.

Primary endpoints, for each cohort:

1. MACE: Mortality, stroke, moderate/major PVL, moderate/severe valve deterioration at 1 year, using VARC-3 criteria (10).

Secondary endpoints, for each cohort:

1. MACE: Mortality, stroke, moderate/major PVL, moderate/severe valve deterioration at 30-day, 3-year, 5-year and 10-year, using VARC-3 criteria (10).
2. Mortality: 30-day, 1-year, 3-year, 5-year and 10-year.
3. Stroke: During admission, 30-day, 1-year, 3-year, 5-year and 10-year, using VARC-3 criteria (10).
4. Moderate or severe PVL: 30-day, 1-year, 3-year, 5-year and 10-year, using VARC-3 criteria (10).
5. Moderate or major valve deterioration: 30-day, 1-year, 3-year, 5-year and 10-year, using VARC-3 criteria (10).
6. Pacemaker-implantation: during admission, 30-day, 1-year, 3-year, 5-year and 10-year.
7. Major bleeding resulting in drop in hgb-level ≥ 1.86 mmol/l and/or erythrocyte transfusion ≥ 2 units: during admission, 30-day, 1-year, 3-year, 5-year and 10-year, modified from BARC type 3-5 criteria (11, 12).
8. 6-minute walk test: baseline, 30-day, 1-year, 3-year, 5-year and 10-year.
9. Other TAVI-related complications: conversion to open surgery during implantation, unplanned use of cardiopulmonary support (CPS), coronary artery obstruction, ventricular septal perforation, mitral valve apparatus damage or dysfunction, cardiac tamponade, valve embolization, valve migration, need for TAVI-in-TAVI deployment, using VARC-3 criteria (10).
10. Other TAVI-related complications: Annulus rupture, Aortic rupture.
11. Endocarditis, 30-day, 1-year, 3-year, 5-year, 10-year.
12. Proportion with successful implantation of the chosen valve. This means no need for more than 1 TAVI valve, no change to another valve than planned during the procedure because it was impossible to implant the valve planned, and no conversion to surgery or procedure-related death.
13. Major vascular access site and access-related complications resulting in endovascular or open surgery using VARC-3 criteria during admission and at day 30 (10).
14. Occurrence of valve thrombosis or severe stenosis (confirmed by TEE, TTE or CT), 30-day, 1-year, 3-year, 5-year and 10-year.
15. Readmission for congestive heart failure: 30-day, 1-year, 3-year, 5-year or 10-year.
16. Increase in renal creatinine level more than to $\geq 200\%$ (AKIN stage 2-3, VARC-3 criteria) or resulting in dialysis (AKIN stage 4) according to VARC-3 criteria: during admission and at day 30 (10).

17. Severity of PVL stratified according to level of annular calcium on CT (low/medium/high) at day 30.
18. Gradient (AO) stratified according to level of annular calcium on CT (low/medium/high) at day 30.
19. Prosthesis-patient mismatch (EOA/body surface area). Severe PPM \leq 0.65 cm²/m². Moderate PPM \leq 0.85 cm²/m², 30-day, 1-year, 3-year, 5-year and 10-year according to VARC-3 criteria (10).
20. Effective orifice area and volume of aortic regurgitation measured by MRI at 1 month (only patients included in MRI sub-study).
21. Leaflet thickening (hypoattenuated leaflet thickening = HALT) or reduced leaflet motion or thrombus assessed by HCT at 1 month and 12 month (only patients included in HCT sub-study).
22. Proportion with moderate or major commissural misalignment on 1 month HCT (only patients included in the HCT sub-study)
23. AMI, 30-day, 1-year, 3-year, 5-year and 10-year according to VARC-3 criteria (10).
24. PCI (not scheduled before TAVI), 30-day, 1-year, 3-year, 5-year and 10-year according to VARC-3 criteria (10).
25. CABG (not scheduled before TAVI), 30-day, 1-year, 3-year, 5-year and 10-year according to VARC-3 criteria (10).
26. Reoperation (TAVR, SAVR, BAV), 30-day, 1-year, 3-year, 5-year and 10-year according to VARC-3 criteria (10).
27. Newly diagnosed atrial fibrillation/flutter, 30-day, 1-year, 3-year, 5-year and 10-year according to VARC-3 criteria (10).

Registration of endpoints:

The majority of endpoints are collected from national registries. An echo core-lab is established to evaluate echo parameters (degree of PVL moderate/severe, valve deterioration, thrombosis). A CT core-lab is established to evaluate CT parameters (leaflet thickening, reduced leaflet motion, leaflet thrombosis, coronary alignment). An MRI core lab is established to evaluate MRI parameters (EOA and volume of aortic regurgitation). A separate core lab is established for analysis of aortaograms (videodensitometry) following TAVI. Procedure-related complications are manually collected from electronic patient files. At each follow-up (1-month, 1-year, 3-year, 5-year, 10-year) each site also monitor events and file them in the ECRF, thus both site-reporting and registry-validation of events. Selected endpoints are adjudicated by an endpoint committee (Stroke, AMI, readmission with heart failure, endocarditis).

Power calculations:

For each cohort (randomized comparison between two valves) the steering committee decides to perform the study with or without interim analyses. In case interim analyses is chosen, a safety committee will compare outcome after inclusion of approximately 1/3 and 2/3 of patients (interim analyses). If one valve is

not clearly inferior, randomization will continue until the complete cohort is included. The size of the cohort is dependent of expected event-rate, chosen non-inferiority margin, number of interim analyses and expected drop-out. See table below. With 2 interim analyses and a non-inferiority margin of 4%, event rate 9% and expected drop out of 5% the sample size should be 1346 patients. If including 1062 patients as planned in cohort B, and with no interim analyses and 5% drop-out, the non-inferiority margin would be 4% if the event-rate is 7% and 4.5% if the event rate is 9%. If the observed event-rate differ significantly from the expected, the steering committee should consider adjusting sample size or non-inferiority margin (see table below).

Table: Various event-rates, non-inferiority margins and sample sizes estimated for non-inferiority studies with and without drop-out, and with and without interim analyses. Power=0.80. Alfa=0.05.

Event rate	Non-inferiority margin	Relative non-inferiority margin	No drop-out, No interim-analysis	No drop-out, 2 interim-analyses	5% drop-out, no interim-analyses	5% drop-out, 2 interim-analyses
Closest non-inferiority margin (1.decimal) if no. of included patients is 1062, without interim-analyses and with 5% drop-out (As planned in cohort B)						
7	≈4.0	0.57				
9	≈4.5	0.50	1009	1017	1062	1071
11	≈5.0	0.45				
13	≈5.3	0.41				
Closest non-inferiority margin (1.decimal) if no. of included patients is 1345, With interim analyses and 5% drop-out (As planned in cohort A)						
7	≈3.6	0.52				
9	≈4.0	0.44	1268	1279	1336	1346
11	≈4.4	0.40				
13	≈4.7	0.36				
Study size if fixed non-inferiority margin = 4%						
7	4	0.57	1008	1017	1062	1070
9		0.44	1268	1279	1335	1346
11		0.36	1514	1527	1594	1607
13		0.31	1750	1764	1843	1857
Study size if fixed non-inferiority margin = 4.5 %						
7	4.5	0.64	796	803	838	845
9		0.50	1002	1011	1055	1064
11		0.41	1198	1208	1262	1272
13		0.35	1382	1394	1455	1467

For the MRI-substudy evaluating the hemodynamics (EOA, aortic regurgitation fraction), the expected EOA is 1.5 (SD 0.54) cm², and the expected regurgitation fraction 0.14 (SD expected to be 0.09). A total of 148 patients are needed to document a difference of 0.25 cm² in EOA (1.5 to 1.25 cm²) and 102 patients to document a difference of 0.05 in expected regurgitation fraction (0.14 to 0.09). The initial plan was to include 166 patients with an expected drop-out of 10% of patients. After inclusion of the first 166 patients in the MRI-substudy, inclusion was on hold for 1 year, and Myval was replaced by Myval Octacor. It was therefore decided to include another cohort in the MRI-substudy, comparing Sapien with Myval Octacor. To account

for higher than expected drop-out, the ethical committee was applied and approved that the MRI-substudy cohort was increased up to 360 patients. A HCT-substudy is performed with expected 850 patients evaluating occurrence of HALT at 1-month and 1-year. This substudy is descriptive.

Criteria used to perform interim analysis before planned or terminate the study before planned:

For each cohort the maximal inclusion period is 3 years, and the first interim analysis (if planned according to the steering committee) will be performed after no later than two years of inclusion. A cohort will also be closed for inclusion, if one of the study valves is retracted from the market or replaced by a new generation of the device.

Number of centers and procedures per center: The prerequisite for initiating a comparison between two valves is that at least 3 centers will randomize from the beginning, that at least 10 centers are expected to randomize in each cohort, and that each center aims at including at least 50 patients per year.

Statistics: Data will be analyzed according to the intention-to-treat principle. Continuous data will be presented as mean \pm SD, and compared using a t-test, if data are normally distributed. If data are not normally distributed the Mann Whitney U test will be used. Categorical variables will be compared using Fischers exact test or Chi-square test as appropriate, and data presented as numbers and percentages. Significance level is $p<0.05$ (double sided). When comparing primary endpoints, a non-inferiority analysis will be used. When comparing secondary endpoints, Cox regression and logistic regression analyses will be used, as appropriate. Kaplan-Meir curves will be used for graphical presentation of time to events.

Data management: Data will be collected and stored according to the Danish data protection legislation. TrialPartner will be used for the Electronic Case Report form (ECRF). Patient and procedural characteristics will be entered in the ECRF following the procedure and at time of discharge. Follow-up (30-day, 1-year, 3-year, 5-year and 10-year) will be conducted mainly registry based (CPR-registry, National patient registry, Invasive registry), but at each follow-up the site will also check for events, and file them in the ECRF. This will ensure two sources for event-registration. Regarding moderate and severe PVL, moderate and severe aortic stenosis, and presence of thrombus or leaflet thickening, data will be entered by the Echo and HCT core labs. MRI findings will be entered by the MRI core lab. TrialPartner is approved by the Danish data regulative, and data entry and access will be logged. When a cohort is terminated, data will be merged and anonymized and a key stored with the CPR-number.

Recruitment of patients and informed consent: Patients admitted for a TAVI procedure will be asked for inclusion in the study. No announcement will be performed. There is no economical compensation to the patients, except that transportation expenses can be covered for the follow-up visits. Patients will receive information regarding the study either in the out-patient clinic, or when they are admitted for preoperative assessment. The information will be given by a nurse, instructed by the investigator, or by the treating physician. Patient information will be written and oral. The patient will be informed that they may have time to consider inclusion, that a relative or a third person may participate, when information regarding the study is given. The patient is informed, that they may withdraw their consent at any time. All patients have been given written and oral information regarding the purpose, procedure, risk and benefit with the study. On

arrival to the operating room, the patient again will be given time to ask any question. A written informed consent is required before randomization.

Withdrawal from the study: A patient can at any time without reason withdraw their consent. The patient will be asked, if previously collected data can be used, and whether it is acceptable to follow them in the registries, even though they don't want to meet to follow-up visits. Otherwise data will be deleted. The patient's decision to withdraw will be filed in the patient record.

Ethical aspects, risk, side effects, benefit and harm when participating in the study:

It is not expected that any risk is associated with participation in the study. The procedures compared are routine procedures and only high-volume centers will participate, and patients will only be included if a heart team conference have found them eligible for treatment with the study valves.

None the less it is important to continuously monitor safety and quality of the valves. The present study will ensure continuous head-to-head comparisons of valves used routinely. There is no potential benefit for the single patient when participating. Scientifically, the benefit is quality assessment of the valves used routinely and publication of long-time follow-up. In case a valve performs inferior to its comparator, appropriate consequences will be taken. Historically, there are examples (Mitroflow surgical valve) that valves used for several years degenerated earlier than expected.

Biobank: No biobank is collected.

Blinding: The study is not blinded.

Data from patient records: As part of the study data on previous disease (hypertension, diabetes, stroke, myocardial infarction, congestive heart failure), age, sex, Echocardiographic findings, HCT-findings will be collected from the patient records. These data will only be used for study purposes, and will be anonymized when the study is terminated. In situations where these data cannot be collected from registries, they will be retrieved from patient records. The purpose is to use these data in anonymous form when publishing the final results.

Data management and approvals: The Danish Data protection legislation will be followed. The study will be filed to the Danish Data protection agency and the local Ethical committee, and filed to www.clinicaltrial.gov before inclusion starts. In Denmark the national board of health will applied for data from the CPR-registry and the national patient registry. Data can be shared in anonymous form for research purposes.

Access to data: Data is stored in TrialPartner. All data is encrypted. Any access or attempt to access data will be logged. Investigator/Institution will allow monitoring or audit from the ethical committee or the data protection agency as well as the national board of health who will be given access to source data and patient records. Investigator is responsible for ensuring that any patient has been given written consent to access source data (patient record).

Safety committee:

A separate safety committee is established for each cohort. The members are physicians not implanting TAVI-valves.

Event committee:

A separate event committee is established to adjudicate selected endpoints (Stroke, AMI, endocarditis, readmission with CHF).

Steering committee:

For each cohort a steering committee is established with one representative from each of the centers randomizing patients in this cohort. The chair is the physician who from the beginning is responsible for this cohort.

Coordinating center:

The research department at Aarhus University Hospital will be the coordinating center, and responsible for establishing a digital CRF for the trial, and responsible for collecting data, monitoring, coordinating safety committee, event committee and steering committee meetings and publications.

Economy/Funding:

Funds will be applied for support of the study. Each of the company's manufacturing TAVI valves will be applied for support. The companies will have no influence on the design or conduction of the study. If a grant is given the Ethical committee will be informed and any contract should be approved by Aarhus University Hospital. No honorary is given to the patients nor to the physicians responsible for the study. Any grant will be used to the conduct of the study, salary to study nurses/secretaries and presentation of data.

So far cohort B has been sponsored by Meril, The Danish Heart Foundation and Vingmed Vicare.

For new cohorts, the company providing the comparator valve will be applied for a grant to sponsor to cover all expenses in the study (payment of site, monitoring, various committee meetings, core-labs).

Publications:

Each cohort will be published after inclusion of 1.346 patients in case interim analysis is decided or 1.062 patients if no interim analysis is decided, independent of the final findings. If a valve is retracted from clinical use, or the safety committee advocates for pre-term termination of randomization, data will be published at this time. First authorship is given to the center with the highest number of included patients. Number of co-authorships to each center is given according to number of included patients. Core-labs are acknowledged with co-authorships. For each cohort, one physician is responsible for initiating the cohort and senior author on the paper. A separate publication will be performed for 30-day, 1-year, 3-year, 5-year and 10-year data.

Reference list:

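### Cohort B has no single pre-specified non-inferiority margin, and the plan lets the margin be changed once the event rate is known

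*Combined protocol and SAP*

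**What the plan says.** - **Power calculations, text.** Cohort size is presented as a function of several choices: "The size of the cohort is dependent of expected event-rate, chosen non-inferiority margin, number of interim analyses and expected drop-out". For cohort B (1062 patients, no interim analyses, 5% drop-out), "the non-inferiority margin would be 4% if the event-rate is 7% and 4.5% if the event rate is 9"%. Neither pair is named as the design.
- **Power calculations, table.** The cohort B block is headed "Closest non-inferiority margin (1.decimal) if no. of included patients is 1062". It lists margins of about 4.0, 4.5, 5.0 and 5.3% at event rates of 7, 9, 11 and 13%. The caption gives "Power=0.80. Alfa=0.05" without saying one- or two-sided.
- **Power calculations, adjustment rule.** "If the observed event-rate differ significantly from the expected, the steering committee should consider adjusting sample size or non-inferiority margin", with a pointer to the same table.
- **Statistics.** "When comparing primary endpoints, a non-inferiority analysis will be used". No margin, confidence limit or one-sided alpha is given. The only significance level is two-sided 0.05.
- **Blinding and Steering committee.** "The study is not blinded". The committee that may adjust the margin has one representative from each randomizing center.

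**The concern.** The margin defines the null hypothesis of a non-inferiority trial. The false-claim rate is defined only against a margin, or a rule for setting the margin, that was laid down before outcome data were seen. The plan has neither for cohort B.

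The direction of the problem also matters. If the test valve is worse, its extra events raise the pooled event rate. In the cohort B block a higher rate goes with a wider margin, so the harm the trial should detect would itself loosen the standard. This bears on the only primary endpoint. A reader of the final paper could not tell whether the margin was chosen before or after the data.

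**Working it through.** **Inputs.** 1062 patients, 5% drop-out, no interims, power 0.80 and the rate/margin pairs, all from Power calculations. Assumed because not stated: 1:1 allocation, equal true rates for the sample size, and a Wald limit with unpooled variance for the risk difference.

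**1. The plan's sample sizes.** n per arm = 2p(1−p)(z_α + z_β)² / m², then divide the total by 0.95.
- 7%, margin 4%, one-sided 0.05: 2 × 0.07 × 0.93 × (1.645 + 0.842)² / 0.04² ≈ 503.1, so 504 per arm, 1008 in total, and 1008/0.95 gives 1062. The table has 1008 and 1062.
- 9%, margin 4.5%: 1002 and 1055. The table has the same.
- All eight fixed-margin rows reproduce within 3 patients at one-sided 0.05. At one-sided 0.025 none does (7%/4% would need 1278 and 1346).

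**2. The margin is an output of the sample size.** Solve m = √(2p(1−p)/504.5) × (1.645 + 0.842) for 1009 evaluable patients. This gives 3.99, 4.48, 4.90 and 5.27% at 7, 9, 11 and 13%. The plan lists 4.0, 4.5, 5.0 and 5.3%.

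**3. One result, two readings.** Take 51/504 versus 58/504 events.
- Difference: 1.39%.
- SE = √[(0.1012 × 0.8988 + 0.1151 × 0.8849)/504] = 1.956%.
- Upper 90% limit: 1.39 + 1.645 × 1.956 = 4.61%.

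This fails at 4.0% and at 4.5%. The pooled rate is 109/1008 = 10.8%, whose nearest table row is 11% with a 5.0% margin, and there the same data pass.

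**4. False-claim rate.** Exact enumeration of all 505 × 505 outcome pairs with 504 per arm. Non-inferiority is claimed if difference + 1.645 × SE is below the margin. The true difference equals the planned margin, so every claim is false. The margin is fixed, or read from the nearest row of the cohort B block.

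| True rates (planned margin) | Margin fixed | Follows pooled rate | Follows control arm | Moves only if pooled rate is outside plan ± 1.96 SE |
|---|---|---|---|---|
| 7% vs 11% (4%) | 5.22% | 8.58% | 6.98% | 7.51% |
| 9% vs 13.5% (4.5%) | 5.19% | 8.26% | 6.94% | 7.28% |
| 12% vs 16.5% (4.5%) | 5.09% | 10.12% | 9.84% | 10.12% |
| 12% vs 16% (4%) | 5.05% | 14.80% | 14.31% | 14.80% |

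Hand check of the first row: the expected pooled rate is 9%, so the margin moves from 4% to 4.5%. SE = √[(0.07 × 0.93 + 0.11 × 0.89)/504] = 1.80%, and Φ(0.5/1.80 − 1.645) ≈ 8.6%.

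The last two rows are the worst cases over control rates from 5% to 18%. They come mainly from a control rate above plan, as the control-arm column shows. With the control rate below plan the rule tightens the margin: 5% vs 9.5% (planned 4.5%) gives 2.9%. At one-sided 2.5%, the pooled-rate column becomes 4.63, 4.46, 5.62 and 8.71%, against about 2.6% with the margin fixed.

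**The case against.** - **The wording is permissive and names sample size first.** Error rises only if the committee widens the margin. This stands, and it is why the figures are scenarios. It does not remove the defect, because the permission has no timing, threshold or direction and could be used only when it helps.
- **A margin that varies with the event rate can be valid.** If a formula in the pooled rate were pre-specified as the hypothesis, error at its own moving boundary stays near nominal (about 4.8% for 5%). This is correct, so a fixed margin is not the only sound design. The plan states no such formula.
- **The table hints at 9%/4.5%.** The cohort B block prints 1009 and 1062 on that row. But 1062 is also the exact figure for 7%/4%, while the fixed 4.5% block gives 1055 at 9%. The table does not settle the choice.
- **The observed rate reads naturally as pooled, and cohort B plans no interim analysis.** This is fair: nothing says the committee sees rates by arm. Nothing excludes it either, and the pooled-rate column already shows inflation without any by-arm look.
- **The worked example depends on alpha.** At one-sided 2.5% its upper limit is 5.22%, which fails at 4.0, 4.5 and 5.0%. True; the example illustrates the one-sided 5% level that the table uses.

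**Conclusion.** The concern holds and should be fixed before any comparative data are read. It is certain that the documents name no single margin, no single expected event rate and no rule for changing the margin in cohort B.

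The size of the effect depends on the scenario. With the control rate on plan, a nominal 5% becomes about 7–9%. With a control rate above plan it reaches about 10% against a planned 4.5% margin, or 15% against a planned 4% margin. It can fall below nominal when the rate is under plan. These figures assume 504 evaluable patients per arm, a Wald limit, unchanged sample size and a margin taken from the plan's own table. The unstated alpha for the non-inferiority test adds to the uncertainty, since the table fits one-sided 0.05 and the Statistics section gives only a two-sided level.

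**What to change.** 1. For each cohort, state one absolute margin with its justification, one expected event rate and the one-sided alpha. For cohort B, say which of the two pairs is the plan. Put the margin and the confidence limit to be used in the Statistics section.
2. Remove the margin from the sentence that allows adjustment. Keep sample-size re-estimation only, from the pooled rate with arms hidden, at a stated time. If the size is left unchanged, report the resulting power.
3. If a rate-dependent margin is really wanted, write its formula and decision rule now as the hypothesis, and show its type I error.
4. Align the Publications section, which ties 1346 or 1062 patients to the interim decision alone. At 9% and 4%, interims account for 1346 − 1335 = 11 of the 284 difference; the other 273 come from a different rate/margin pair.

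**Cost.** The change is wording only, but a fixed margin loses power if events are frequent. With 1062 patients and a 4.5% margin, power at one-sided 5% is about 74% at an 11% rate and 68–69% at 13% (about 63% and 57% at one-sided 2.5%). Keeping 80% power takes 1262 or 1455 patients by the plan's own table, which is 200 or 393 more. Those patients must fit within the 3-year inclusion limit and the rule closing a cohort when a valve is replaced by a new generation. The latter matters because the MRI sub-study text already reports such a replacement for Myval.

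### Patients added to the MRI substudy are Sapien versus Myval Octacor, so they cannot make up drop-out in the Sapien versus Myval comparison, which had almost no reserve above its stated 148

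*Combined protocol and SAP*

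**What the plan says.** The paragraph on the MRI substudy, after the sample-size table in the Power calculations section, gives these planning values: "the expected EOA is 1.5 (SD 0.54) cm²" and "the expected regurgitation fraction 0.14 (SD expected to be 0.09". The resulting sizes are "A total of 148 patients are needed to document a difference of 0.25 cm² in EOA" and "102 patients to document a difference of 0.05 in expected regurgitation fraction (0.14 to 0.09". The initial plan was 166 patients, allowing for 10% drop-out.

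The history follows: "After inclusion of the first 166 patients in the MRI-substudy, inclusion was on hold for 1 year, and Myval was replaced by Myval Octacor". The protocol gives this as the reason for adding a further MRI cohort that compares Sapien with Myval Octacor. The next sentence covers the allowance "for higher than expected drop-out, the ethical committee was applied and approved that the MRI-substudy cohort was increased up to 360 patients".

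The plan does not give the observed drop-out, the split of the 360, a target for the second comparison, or a rule on whether the two Myval generations are analysed apart or together. Secondary endpoint 20 lists the MRI measures at 1 month without naming a device generation. The Statistics section specifies a t-test for normally distributed continuous data and a Mann-Whitney test otherwise. The section on criteria for early interim analysis or termination closes a cohort when a study valve is replaced by a new generation.

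**The concern.** The added patients are recruited after the device change and are randomized to Sapien or Octacor. They can size that new comparison, but they cannot restore patients lost from Sapien versus Myval, which is fixed at 166. The planned allowance of 10% left that comparison almost exactly at its requirement, and the plan itself reports that drop-out was higher than expected.

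Two things are at stake. First, the 148 and its 0.25 cm² difference remain the only stated precision for the EOA comparison, although the first comparison may no longer reach them. Second, with one total for two device comparisons and no analysis rule, Octacor could be compared with Sapien patients scanned before the one-year hold, or both generations could be pooled. The first contrast would be partly non-concurrent. The second would estimate an average over two devices.

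**Working it through.** **Inputs.** EOA: SD 0.54 cm², difference 0.25 cm². Regurgitation fraction: SD 0.09, difference 0.05. Enrolment: 166, then up to 360. Planned drop-out: 10%. All are from the Power calculations section. Error rates: "Power=0.80. Alfa=0.05" heads the main sample-size table, and I assume it also applies to the MRI substudy. The Statistics section has "Significance level is $p<0.05$ (double sided". No allocation ratio is stated, so I assume 1:1.

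**Reproducing the plan's figures.** n per arm = 2 × (1.96 + 0.8416)² × SD² / difference².

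- EOA: 2 × 7.849 × 0.54² / 0.25² = 73.2, so 74 per arm and 148 in total.
- Regurgitation fraction: 2 × 7.849 × 0.09² / 0.05² = 50.9, so 51 per arm and 102 in total.
- Drop-out: 74 / 0.90 = 82.2, so 83 per arm and 166 in total.

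All three match. A one-sided calculation gives 116 for EOA and does not match.

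**Reserve in each set.**

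- First set, Sapien versus Myval: 166 − 148 = 18 patients, or 18/166 = 10.8%. Losses of 17 (10.2%) or 18 (10.8%) exceed the planned 10% and still leave 149 or 148. Nineteen losses (11.4%) leave 147.
- Added set, Sapien versus Octacor: 360 − 166 = 194, and 1 − 148/194 = 23.7%.
- Regurgitation fraction in the first set: 1 − 102/166 = 38.6%.

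The enlargement therefore gives a wide drop-out allowance to the second comparison and none to the first.

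**Size of the effect on Sapien versus Myval.** The drop-out values are assumptions, since the plan gives none. Power is for 0.25 cm² by a two-sample t-test. The detectable difference at 80% power is 2.80 × 0.54 × √(4/N).

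| Assumed drop-out | Evaluable N | Power | Detectable difference | At least 102? |
|---|---|---|---|---|
| 15% | 141 | 78% | 0.26 cm² | yes |
| 20% | 133 | 75% | 0.26 cm² | yes |
| 30% | 116 | 70% | 0.28 cm² | yes |

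The normal approximation gives about 0.5 to 1 percentage point more power in each row. Just below 148 the loss is negligible: at 147 the normal approximation still gives 80.1%.

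**What covariate adjustment could recover.** With correlation r between baseline annulus size and EOA, the required total is about 148 × (1 − r²). The documents give no value for r, so this is a range:

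- r = 0.2: 142
- r = 0.3: 135
- r = 0.4: 124
- r = 0.5: 111

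At r = 0.4, 1 − 124/166 = 25.3%, so 80% power would be kept up to roughly 24–25% drop-out. At 30% drop-out (116 evaluable) it would not be restored.

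**The case against.** The strongest reply is that the plan never says the added patients replace losses from the first 166. It gives the device change first, as the reason for another cohort. The drop-out sentence can be read as explaining why that cohort may reach 194 instead of another 166. On that reading the second comparison is sensibly sized. This stands, and it means the enlargement should not be described as made only to cover drop-out. It does not help the first comparison, which is then left with no stated allowance for its excess loss.

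A reader might infer that Sapien versus Myval is already below 148. The documents do not show this: they say only that drop-out exceeded expectation, and 17 or 18 losses would still leave 149 or 148.

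A reader might also infer that the single figure of 360 signals a pooled analysis. The text does not support this either. It introduces the Octacor patients as a further cohort with its own comparison, and nothing proposes pooling. What is missing is the detail: the split, the targets and the analysis rule.

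It is also fair to say that no stated figure is arithmetically wrong, that a confidence interval will show the precision achieved, and that this is one secondary endpoint in a substudy. These points limit the weight of the concern but do not remove it, because the stated planning precision would still stand uncorrected for the first comparison.

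**Conclusion.** The point holds in a limited form. The added patients, up to 194, cannot repair losses in Sapien versus Myval, and that comparison misses its stated 148 at 19 or more losses of 166. A shortfall is likely, given drop-out above 10% and a break-even of 10.8%, but it is neither certain nor quantified in the plan.

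If it occurred, the effect is moderate: power falls from 80% to the range 70–78%, or the detectable difference rises from 0.25 to 0.26–0.28 cm², for assumed drop-out of 15% to 30%. The regurgitation-fraction requirement is safe over that range, and the primary endpoint is not affected. The conclusion assumes 1:1 allocation, two-sided 5% significance with 80% power for the substudy (both supported by the reproduced 148), and drop-out meaning patients without an evaluable MRI.

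**What to change.** 1. Report the observed drop-out among the first 166 and the split of the 360. Restate the detectable EOA difference or the power for Sapien versus Myval from its actual evaluable number.
2. State that each Myval generation is compared only with the Sapien patients randomized concurrently with it. Any pooled estimate should be stratified by generation and labelled secondary.
3. Replace the unadjusted t-test for EOA with a comparison adjusted for baseline CT annulus size, provided it is recorded; the section on data from patient records says HCT findings are collected. State that the gain depends on a correlation that is not yet known.

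The cost is some wording, a slightly less favourable stated figure for the first comparison and a little more analysis. No added patients are needed.
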